5.6.3 Additional Safety Assessments

5.6.3.1 Clinical laboratory evaluations

Starting from Visit 2, blood specimens for routine assay of hematology and clinical chemistry testing will be analyzed by the local laboratory affiliated with the site. The individual laboratory parameter result data will not be collected in the eCRF; however, the Investigator will report any out of range results judged to be clinically significant as an AE.

No laboratory data will be summarized in tables. Laboratory test for PDILI will be listed if it occurred. Blood sample collection for pharmacokinetics for PDILI and suspected hepatic event for PDILI will be listed if it occurred.

5.6.3.2 Vital Signs

Vital signs (systolic blood pressure [SBP], diastolic blood pressure [DBP], and pulse rate) will be assessed in a semi-supine position after 5 minutes rest throughout the study, according to the tabular schedules of procedures in Section 1.3 of protocol. Body weight and height will also be assessed throughout the study, according to the tabular schedules of procedures. BMI will be derived as defined in Section 5.1.2.2.

5.6.3.2.1 Vital Sign Values Over Time

All summaries of vital signs, body weight, height, and BMI will only summarize variables planned based on the protocol. However, both planned and unplanned variables will be provided in participant data listings.

Observed values of SBP, DBP, pulse rate, body weight, height and BMI will be summarized for each scheduled visit. Change from Baseline for SBP, DBP, pulse rate, body weight, height, and BMI will be summarized for all scheduled post-baseline visits.

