e The End of Study Period starts after the Early Termination Visit or Termination Visit. In case of LCM withdrawal and taper, the Investigator may add any other AED during the End of Study Period, following the Investigator's medical judgment. A Final Visit will be completed 30 days (-1/+3 days) after the final dose of LCM.

f An Unscheduled Visit may be performed at the discretion of the Investigator. Such visits may be necessary if the dosage of LCM is to be adjusted in between scheduled visits. If an Unscheduled Visit is needed, then the assessments noted will be performed. Additional assessments may be performed at the Investigator's discretion. Please refer to footnote "o" below regarding participants which meet the conditions for administration of the C-SSRS. Participants meeting these conditions will have the C-SSRS administered if the Unscheduled Visit is due to a safety or efficacy reason.

g The total number of weeks in the Treatment Period will vary between individual study participants, as this study involves a Treatment Period of approximately up to 205 weeks, depending upon the age of the study participant. Scheduled clinic visits will occur approximately every 26 weeks relative to EP0151 Visit 1 date.

h The week of the Termination Visit/Early Termination Visit will vary between individual study participants, depending on study participant age (for Termination Visit) or weeks in study when early termination occurs (for Early Termination Visit).

i Demography information will be documented from the parent studies EP0034 or SP848.

j Starting from Visit 2, blood specimens for routine assay of hematology and clinical chemistry testing will be analyzed by the local laboratory affiliated with the site. The individual laboratory parameter result data will not be collected in the eCRF; however, the Investigator will report out of range results judged to be clinically significant as an AE.

k Designated procedures conducted at Visit 13/Termination Visit of EP0034 or SP848 will serve as the Baseline data for EP0151.

l The IXRS should be called for any cases of dose adjustment.

m Systolic and diastolic blood pressure and pulse rate will be measured in a semi-supine position after 5 minutes rest.

n Dispensing of LCM will be done at the Termination Visit/Early Termination Visit only if tapering of LCM is required.

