### **Age**

1. Participant is male or female, aged <6 years at the time of signing the Informed Consent Form (ICF).

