## **9.2        General statistical considerations**

Descriptive statistics will be used to provide an overview of the primary variables. For categorical parameters, the number and percentage of study participants in each category will be presented. The denominator for percentages will be based on the number of study participants appropriate for the purpose of analysis. For continuous variables, descriptive statistics will include number of study participants, mean, standard deviation, median, minimum, and maximum. No statistical hypothesis testing will be performed. Baseline values for primary variables will be determined from Baseline values of the EP0034 or SP848 study, unless otherwise noted.

All computations for the analyses will be performed using SAS® version 9.4 or later (SAS Institute, NC, USA).

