## **9.3        Planned safety analyses**

### **9.3.1      Safety analyses**

Treatment-emergent AEs will be defined as those events which started on or after the date of first dose of LCM in EP0151, or events for which severity worsened on or after the date of first dose of LCM in EP0151. Adverse events which occur within 30 days after final dose of LCM in EP0151 will be considered treatment-emergent.

Adverse events will be coded using the Medical Dictionary for Regulatory Activities® (MedDRA). Pretreatment AEs, TEAEs, non-serious TEAEs, withdrawals due to TEAEs, withdrawals due to SAEs, and SAEs will be tabulated by system organ class and preferred term. The incidence of TEAEs will also be summarized by intensity and by relationship to LCM. In addition, all AEs will be listed.

Long-term use of LCM will be assessed by modal daily dose (mg/kg/day) and maximum daily dose (mg/kg/day). These doses will be summarized using descriptive statistics, along with duration of exposure (days).

Actual measurements and changes from Baseline in vital signs, body weight, height, and calculated BMI will be summarized descriptively by visit. In addition, shift tables may be used to evaluate the number and percent of study participants having a different post-Baseline status when compared with their Baseline status.

The endpoints for assessment of long-term use include TEAEs, study participant withdrawals due to TEAEs and SAEs, modal daily dose, and maximum daily dose. Available data related to these measurements will be presented in participant data listings.

Responses to the C-SSRS will be presented in participant data listings.

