1.2 Study design

EP0151 is a multi-center, long-term, open-label, follow-up study to assess the long-term use of LCM oral solution (a formulation suitable for administration to children; also referred to as syrup) for pediatric study participants \leq 6 years of age with epilepsy who have completed either EP0034 or SP848.

Study participants who complete EP0034 or SP848 will be offered participation in EP0151 and will have access to open-label follow-up treatment with LCM. Approximately 80 to 100 study participants are estimated to be eligible for enrollment.

Visit 1 for EP0151 will be the same as Visit 13 in EP0034 or SP848. Clinic visits will be scheduled approximately every 26 weeks relative to the EP0151 Visit 1 date. A visit window of ± 7 days relative to Visit 1 is applicable for all regularly scheduled visits.

All study participants in EP0151 will receive LCM. The Investigator may maintain the study participant's LCM dose from previous studies EP0034 or SP848, decrease the dose in decrements of 2mg/kg/day per week to a minimum dose of LCM 2mg/kg/day, or increase the dose in increments of 2mg/kg/day per week up to a maximum dose of LCM 12mg/kg/day or 600mg/day, whichever is lower, administered twice per day (BID).

This study involves a Treatment Period of approximately up to 205 weeks, depending on the age of the study participant, and an End of Study Period of approximately 8 weeks (including a

Taper Period and a Safety Follow-Up Period). Study participants who reach the end of the study and choose to continue treatment with LCM may be immediately prescribed LCM. The Termination Visit at the end of the Treatment Period will be the last study visit completed for study participants who continue treatment with prescribed LCM. Study participants who choose not to continue with LCM treatment and who are taking a dose of 3mg/kg/day or higher will enter an End of Study Period following completion of the Termination Visit or Early Termination Visit, and will gradually taper from LCM treatment during the Taper Period; a Final Visit will be conducted 30 days after the final dose of LCM.

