5.1.2.1.6 Definition of Baseline values

Baseline is defined as the last non-missing value collected prior to the first dose of LCM in the first LCM study. The Baseline values in EP0034 and SP0848 will be used as Baseline for safety variables in EP0151, if not stated otherwise. Visit 13/Termination Visit of EP0034 or SP848 will be Visit 1, Week 0 for EP0151. The vital signs measured after the 3 minute measurement in supine position of EP0034 at Visit 13/Termination Visit will be used as vital signs at Visit 1, Week 0 for EP0151.

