5.6.3.2.2 Individual Participant Changes of Vital Sign Values

Markedly abnormal (MA) values are defined as those MA values at scheduled or unscheduled visits which occur on or after the first EP0151 LCM administration through to the end of the study. While referring to the MA criteria, age at time of assessment should be considered by adding time between informed consent and the visit date.

The number and percentage of participants with a MA value, MA low value, and MA high value, at each post-Baseline visit and Final Visit, for which SBP, DBP, pulse rate, and body weight are scheduled to be assessed, will be presented. Percentages will be relative to the number of participants with a value at each time point.

The abnormal vital sign criteria are defined as follows:

Table 5-1: Vital signs abnormality criteria

Parameter	Age Range	Abnormality Criteria
Pulse Rate (beats/minute)	6m - <3y	<90 >150
	3y - <12y	<60 >130
SBP (mmHg)	6m - <3y	<70 >120
	3y - <12y	<80 >140
DBP (mmHg)	6m - <3y	<45 >75
	3y - <12y	<50 >80
Body Weight	1m - <17y	<3% or >97% of the normal body weight growth curve ranges ^a based on gender and the age of participant on date of weight assessment

Abbreviations: m=months, y=years. A month is defined as 28 days; a year is defined as 365.25 days.

^a Source: <http://www.cdc.gov/growthcharts/>.

A participant data listing of all vital signs for participants with an AE mapped to the PT bradycardia will be presented.

A participant data listing of all vital signs values including body weight, height, and BMI for all participants will be presented. A separate listing including MA vital signs values will also be presented. Vital signs for PDILI will be listed if it occurred.

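### Weight, height and BMI change is summarised only as raw change from Baseline, so slowed growth can look like ordinary gain; add age- and sex-specific z-scores

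*SAP*

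**What the plan says.** SAP 5.6.3.2.1 plans observed values at each scheduled visit and then: "Change from Baseline for SBP, DBP, pulse rate, body weight, height, and BMI will be summarized for all scheduled post-baseline visits". Protocol 9.3.1 plans the same: "Actual measurements and changes from Baseline in vital signs, body weight, height, and calculated BMI will be summarized descriptively by visit". It also allows shift tables as an option, but the SAP's vital-sign sections specify none.

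The reference point is set in SAP 5.1.2.1.6: "Baseline is defined as the last non-missing value collected prior to the first dose of LCM in the first LCM study". On duration, SAP 1.2 says: "This study involves a Treatment Period of approximately up to 205 weeks, depending on the age of the study participant". Participants are under 6 years at consent (Protocol 5.1), and summaries are also split by age at entry, 2 to <4 and 4 to <6 years (SAP 5.1).

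The one growth-referenced output is the body-weight row of SAP Table 5-1, which flags values "<3% or >97% of the normal body weight growth curve ranges" by gender and age and cites the CDC growth charts. Pulse and blood pressure have markedly abnormal (MA) limits in two age bands in the same table. Height and BMI have no age-referenced output.

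**The concern.** Weight and height rise with age in this age range whether or not the drug does anything. A table of mean change in kg or cm therefore has a positive expected value under normal growth, and usually a positive one under slowed growth too. Nothing in the table tells the reader which of the two is being shown. All participants receive lacosamide, so there is no concurrent group to supply the expected change. Reference growth is the only comparator available, and the SAP applies it only to a weight flag.

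The SAP itself treats growth as worth watching. Decreased appetite, hypophagia, diet refusal and food aversion are among the other significant AEs in Table 6-1, and SAP 5.6.2 sets up a medical review of growth-related TEAEs. That route depends on someone reporting an event. The measured weights and heights are the objective data that should support it, and as summarised they do so poorly.

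**Working it through.** The plan gives no growth rate, SD or expected change, so it has no figure of its own to reproduce on this point. The checks below use its durations and percentile limits; everything else is marked as an assumption.

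**1. Duration.** 205 + 4 + 30/7 = 213.3 weeks, which agrees with the approximately 213 weeks stated. In years, 205 × 7 / 365.25 = 3.93. Time in the parent study since Baseline comes on top and is not stated.

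**2. Raw change under normal growth.** Assumed gain: 1.5 to 3 kg and 5 to 9 cm per year.

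| Time since Baseline | Weight | Height |
|---|---|---|
| 3.93 years (EP0151 only) | +5.9 to +11.8 kg | +19.6 to +35.4 cm |
| 4.93 years (1 parent-study year assumed) | +7.4 to +14.8 kg | +24.6 to +44.4 cm |
| 5.93 years (2 parent-study years assumed) | +8.9 to +17.8 kg | +29.6 to +53.4 cm |

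The first row is the longest case, a very young entrant who stays to age 6. A child entering at 4 has about 2 years in EP0151: 2 × 1.5 = +3 kg to 2 × 3 = +6 kg.

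**3. Slowed growth on the same scale.** A child gaining 1 kg per year for 2 years shows +2 kg. Against +3 to +6 kg expected, the shortfall is 1 to 4 kg, yet the table entry is still a gain.

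**4. What the weight flag sees.** Normal quantiles: 3rd percentile z = −1.881, 10th z = −1.282, 75th z = 0.674.

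- 75th to 10th percentile: 0.674 + 1.282 = 1.96 SD, never flagged.
- 50th to 3rd percentile: 1.88 SD, not flagged, because the limit is below 3%.
- 75th to 3rd percentile: 2.56 SD, not flagged.
- Reference population: 3% + 3% = 6% flagged at any visit, or 4.8 of 80 and 6.0 of 100.

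The flag is a status at a visit. A child already below the 3rd percentile before lacosamide counts in the same way as one who has fallen there.

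**5. After the fix.** Under reference growth the expected mean change in z-score is about 0 at every visit. With n = 80 to 100 and an assumed SD of z-score change of 0.5 to 1.0, the 95% half-width is 1.96 × SD / √n:

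- smallest: 1.96 × 0.5 / √100 = 0.10
- largest: 1.96 × 1.0 / √80 = 0.22

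This holds at full attendance and widens at late visits. The child falling from the 75th to the 10th percentile would show a change of −1.96.

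**The case against.** The strongest reply is that more is planned than the raw-change table. The MA-low weight count uses age and gender and can rise if growth falters. Summaries are split by entry age. Every weight, height and BMI is listed, so z-scores could be derived later. Growth is neither an objective nor an endpoint, all analyses are descriptive, and the SAP follows Protocol 9.3.1. All of this stands. It means the information is obscured rather than lost, and that the weight output is not blind. It does not supply a growth-referenced change for weight, or anything growth-referenced for height or BMI.

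Four stronger readings are tempting, and the documents do not support them.

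- A reader might infer that normal growth hides any drug effect. That needs a growth rate, an SD and an effect size, and the documents give none. For BMI they do not even show a direction of change with age.
- A reader might infer from Table 5-1 that mean pulse falls by 20 to 30 beats/min at age 3, because the limits move from 90–150 to 60–130. These are screening cut-offs with a step at one birthday, and they do not give mean pulse by age. Age-banded MA tables for pulse and blood pressure are already planned. Stratifying further at age 3 would leave the younger stratum almost empty after about Week 52, since the SAP's entry-age groups start at 2 years.
- A reader might blame the pre-lacosamide Baseline. A later Baseline would not cure the problem, because up to 3.93 years of growth falls inside EP0151, and it would miss any effect already present from the parent study.
- A reader might expect z-scores to isolate a drug effect. Without a control arm they cannot. They remove expected reference growth only; underlying disease and changes in concomitant antiepileptic drugs remain.

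**Conclusion.** The point holds for weight, height and BMI. Their change is planned only on the raw scale, where normal and slowed growth in weight and height can both appear as gain. The one growth-referenced output is a per-visit weight status that allows falls of about 2 SD to go unflagged and does not cover height or BMI.

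The absence of any growth-referenced change is a matter of what the documents say and needs no assumption. The sizes in kg and cm rest on the assumed growth rates, and the precision figures on the assumed SD of z-score change. For pulse and blood pressure, the most that follows is that mean change should be read against age.

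This is a worthwhile and inexpensive improvement to the reporting of non-primary safety variables. No primary endpoint is affected.

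**What to change.** In SAP 5.6.3.2.1:

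- Add age- and sex-specific z-scores for weight, height and BMI from the CDC source already cited under Table 5-1. Summarise observed values and change, both from Baseline and from Visit 1. Where the reference does not cover the child's age at Baseline, give change from Visit 1 only.
- Add a descriptive count of children with a marked fall in weight or height z-score. A fall of at least 1 is an example; the documents set no threshold, so the sponsor should choose and state one in advance.
- Keep the raw summaries, and note that mean change in pulse and blood pressure should be read against age.

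While editing, reconcile the Baseline definitions. A footnote to Protocol Table 1-1, attached to blood pressure, pulse, weight and height, says: "Designated procedures conducted at Visit 13/Termination Visit of EP0034 or SP848 will serve as the Baseline data for EP0151". SAP 5.1.2.1.6 uses the pre-lacosamide value instead. Protocol 9.2 points to the parent-study Baseline, but only for primary variables: "Baseline values for primary variables will be determined from Baseline values of the EP0034 or SP848 study, unless otherwise noted". SAP 6.2 declares no changes from the protocol. Reporting change from both points makes the choice visible, but the text should name which one is called Baseline.

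The cost is SAP wording and a modest amount of programming. No new data are needed: weight and height are measured at scheduled visits, and the weight flag already requires gender and age at assessment. The CDC source is at present cited only for weight, so the height and BMI references must be named.

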5.6.3.2.2 Individual Participant Changes of Vital Sign Values

Markedly abnormal (MA) values are defined as those MA values at scheduled or unscheduled visits which occur on or after the first EP0151 LCM administration through to the end of the study. While referring to the MA criteria, age at time of assessment should be considered by adding time between informed consent and the visit date.

The number and percentage of participants with a MA value, MA low value, and MA high value, at each post-Baseline visit and Final Visit, for which SBP, DBP, pulse rate, and body weight are scheduled to be assessed, will be presented. Percentages will be relative to the number of participants with a value at each time point.

The abnormal vital sign criteria are defined as follows:

Table 5-1: Vital signs abnormality criteria

Parameter	Age Range	Abnormality Criteria
Pulse Rate (beats/minute)	6m - <3y	<90 >150
	3y - <12y	<60 >130
SBP (mmHg)	6m - <3y	<70 >120
	3y - <12y	<80 >140
DBP (mmHg)	6m - <3y	<45 >75
	3y - <12y	<50 >80
Body Weight	1m - <17y	<3% or >97% of the normal body weight growth curve ranges ^a based on gender and the age of participant on date of weight assessment

Abbreviations: m=months, y=years. A month is defined as 28 days; a year is defined as 365.25 days.

^a Source: <http://www.cdc.gov/growthcharts/>.

A participant data listing of all vital signs for participants with an AE mapped to the PT bradycardia will be presented.

A participant data listing of all vital signs values including body weight, height, and BMI for all participants will be presented. A separate listing including MA vital signs values will also be presented. Vital signs for PDILI will be listed if it occurred.

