5.1.2.3 Exposure duration

The overall duration of LCM exposure for each participant will be calculated as the date of the last dose of LCM minus the date of the first dose of LCM plus 1 day. Gaps in treatment or days with unknown dosing will not be subtracted from the duration of exposure. The duration of LCM exposure will be summarized descriptively, separately, as a continuous parameter (in days) and as a categorical parameter, where categories will be defined using the following cumulative 6-month intervals for the Treatment Period: >0 months, >6 months, >12 months, >18 months, >24 months, >30 months, >36 months, >42 months, and >48 months, where 1 month is defined as 28 days.

Participant-years of LCM exposure in the study is calculated as the duration of exposure (days) divided by 365.25.

Participant-years of LCM exposure will be summarized using the following cumulative 6-month time intervals for the Treatment Period: >0 months, >6 months, >12 months, >18 months, >24 months, >30 months, >36 months, >42 months, and >48 months.

Participant-months of exposure will be calculated as the sum of days of exposure divided by 28.

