6 SUPPORTING DOCUMENTATION

6.1 Appendix 1 Non-key analysis specifications

6.1.1 Baseline characteristics and demographics

Demographics and baseline characteristics will be summarized descriptively for the SS. The summary comprises age (years) at entry into EP0151, age (years) at entry into first pediatric study, and age at entry into EP0151 categorized as (24 months - <12 years), racial group (American Indian/Alaskan Native, Asian, Black, Native Hawaiian or Other Pacific Islander, White, and Other/Mixed), ethnicity (Hispanic or Latino, and not Hispanic or Latino), weight (kg), height (cm) and BMI (kg/m^2). The number of participants and percentage for age groups, gender and countries will also be presented for the SS.

Demographic data will also be listed for the SS.

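### SAP Table 5-1 pairs a 28-day month with a 365.25-day year and gives no age unit for the growth-curve weight lookup, so a lookup in the SAP's own months would overstate age by up to 8.7%

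*SAP*

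**What the plan says.** SAP Section 5.6.3.2.2 defines the markedly abnormal (MA) vital-sign criteria in Table 5-1. For body weight, a value is flagged when it lies below the 3% or above the 97% limit of the "growth curve ranges", applied "based on gender and the age of participant on date of weight assessment". The row covers ages from 1 month to under 17 years.

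The footnote opens with "Abbreviations: m=months, y=years" and continues: "A month is defined as 28 days; a year is defined as 365.25 days".

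For all MA criteria, the section says that "age at time of assessment should be considered by adding time between informed consent and the visit date". It gives no unit for the starting age or for the added time, and no unit for the growth-curve lookup.

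Elsewhere, SAP Section 6.1.1 reports "age (years) at entry into EP0151". The 28-day month also appears in Section 5.1.2.3 ("where 1 month is defined as 28 days"), in the completer cohorts of 5.1.2.5 and in the disposition intervals of 5.2. In those places it only counts time on study.

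**The concern.** A 28-day month does no harm as a way of counting exposure. As a unit of age it does harm once age in months is compared with an external reference curve that runs on calendar age. A programmer who reads the footnote as governing the table, and who enters the curves by age in months, would compare each child with children older than that child. Another programmer, working in years, would not. Both would be following the SAP, and their MA weight tables would differ.

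The MA weight table matters because it is the only growth summary in the plan that is referenced to age. SAP Section 5.6.3.2.1 otherwise summarises weight, height and BMI as observed values and changes from Baseline. The study has one arm, so no control group would reveal a systematic shift in the flags. SAP Table 6-1 lists decreased appetite and hypophagia among the other significant AEs, so low-weight flags are likely to be read with some attention.

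**Working it through.** **Inputs from the documents**
- Month = 28 days and year = 365.25 days (SAP Table 5-1 footnote).
- Youngest SAP age group starts at 2 years (SAP 5.1). Participants normally finish around age 6 (protocol 4.1).
- Treatment lasts up to about 205 weeks: "This study involves a Treatment Period of approximately up to 205 weeks" (SAP 1.2).
- The plan states no expected flag rate, so there is no figure of its own to reproduce.

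**1. Do the two units agree?** 12 × 28 = 336 days, against 365.25. They do not. The month consistent with the stated year is 365.25/12 = 30.4375 days, and 30.4375/28 = 1.087. Age in 28-day months therefore exceeds true age in months by 8.7%.

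**2. Does the 28-day month do anything else in Table 5-1?** The only bounds in months are 1m (weight) and 6m (pulse and blood pressure). With the youngest group starting at 2 years, neither bound separates any child. The bounds that can matter (3, 12 and 17 years) use the 365.25-day year. In this table the 28-day month therefore either has no effect or acts only through the weight lookup.

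**3. Age error if the whole age is converted.** Error = years × 365.25/28 − years × 12.

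| True age | 28-day months | True months | Error |
|---|---|---|---|
| 2 y | 26.1 | 24 | +2.1 |
| 3 y | 39.1 | 36 | +3.1 |
| 4 y | 52.2 | 48 | +4.2 |
| 5 y | 65.2 | 60 | +5.2 |
| 6 y | 78.3 | 72 | +6.3 |

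**4. Age error if only the time since consent is converted** (starting age correct). Error = days/28 − days/30.4375, with days = 7 × weeks.

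| Week | 28-day months | True months | Error |
|---|---|---|---|
| 0 | 0 | 0 | 0 |
| 26 | 6.5 | 6.0 | +0.5 |
| 52 | 13.0 | 12.0 | +1.0 |
| 104 | 26.0 | 23.9 | +2.1 |
| 205 | 51.25 | 47.15 | +4.1 |

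For a child entering at 2 years, true age at Week 205 is 24 + 47.15 = 71.15 months, and the overstatement is 4.1/71.15 = 5.8%.

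**5. Age error if age is held in exact years or days:** 0 at every visit.

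**6. What this could do to the flags (illustration only).** The documents give neither weight gain nor spread. Assume normally distributed weights, a gain g of 1.5 to 2.5 kg/year, and an SD of 1.5 kg at 2 years that changes linearly to between 1.5 and 4.5 kg at 6 years. Let a be true age, a′ the overstated age and z = −1.881 the 3% point. Then
- low rate = Φ([g(a′ − a) + z·SD(a′)]/SD(a))
- high rate = 1 − Φ([g(a′ − a) − z·SD(a′)]/SD(a))

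Both rates are 3% when a′ = a. Whole-age conversion gives:

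| | Age 2 | Age 6 |
|---|---|---|
| Low flags, range | 3.1–5.6% | 3.1–15.6% |
| High flags, range | 1.0–2.0% | 0.3–1.3% |
| Low flags, g = 2, SD 1.5 to 2.5 kg | 4.4% | 5.9% |
| Low flags, g = 2, SD 1.5 to 4.5 kg | 3.5% | 3.5% |

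Converting only the time since consent, for entry at 2 years, gives 3.0–9.5% low and 0.7–1.8% high at Week 205. No scenario moves the flags the other way. The size of the shift, and whether it rises with age, depend on the assumed gain and SD.

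**The case against.** The strongest reply is that the SAP nowhere prescribes a lookup in 28-day months. The footnote explains the abbreviations in the Age Range column, and entry age is reported in years. An analyst who stays in years or days makes no error. This stands: the SAP leaves an ambiguity and does not state a wrong calculation. It does not dispose of the point, because the only month the SAP defines for this table is the wrong one for age.

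A reader might go further and infer several things that the documents do not support:
- **Every child is treated as 8.7% too old.** That requires the whole age to be converted. The section builds age by adding elapsed time to the age at consent, so possibly only the added part is affected, or nothing.
- **False low flags rise with follow-up and imitate a drug effect on growth.** The age error in months does grow under both conversions. The flag rate need not: under whole-age conversion it is flat when the SD grows in proportion to age. Each visit also pools children of different ages.
- **Age is also understated because it starts from completed years.** The SAP does not say this. It leaves the precision of the starting age unstated, which is missing detail. If completed years were used, the error would run the other way and could offset this one.
- **Pulse and blood-pressure flags are affected.** The 28-day month does not reach them (step 2).

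It is also fair to say that growth is covered elsewhere, by changes from Baseline, full listings and medical review of growth-related TEAEs. None of these depends on the 28-day month.

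**Conclusion.** The point holds as a specification defect. Table 5-1 contains two incompatible units of age, and the unit for the weight lookup is not stated. If the SAP's own month is used there, age is overstated by up to 8.7%: by 2.1 months at 2 years and 6.3 months at 6 years for whole-age conversion, or by 0 at Week 0 and about 4.1 months at Week 205 if only time since consent is converted. Provided the reference limits rise with age, this shifts MA weight flags toward low and away from high. With exact years or days the error is zero.

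Neither the effect on flag rates nor its trend over visits can be determined from the documents, and the rates shown above are not estimates for this trial. Exposure is confined to the descriptive MA weight table and listing. No primary endpoint is touched. The correction is worth making because it is cheap and removes a stated unit that would bias this summary if applied as written.

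**What to change.** In SAP Section 5.6.3.2.2:
- Delete the 28-day month from the Table 5-1 footnote.
- State that age at assessment for the growth-curve lookup is computed from exact elapsed days, with years = days/365.25 and months = days/30.4375.
- State that the calculation starts from birth date or, where the full date is not held, from an unrounded age at consent.

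Keep the 28-day month only for the exposure, completer-cohort and disposition intervals (SAP 5.1.2.3, 5.1.2.5 and 5.2).

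The cost is one footnote, one sentence and a small programming change. No new data and no protocol amendment are needed.
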